11.1.4. WHO Functional Class

WHO Functional Class assessment, as defined in [Table 3](#), will be assessed by the clinical Investigator in Part 1 at Screening, Baseline, Weeks 2, 6, 10, 14, and 18, including early discontinuation In Part 2 at Week 16 and 32 and 52.

Table 3: WHO Functional Classification

Class	Subject Symptoms
Class I*	Patients with pulmonary hypertension but without resulting limitation of physical activity. Ordinary physical activity does not cause undue dyspnea or fatigue, chest pain or near syncope.

Class II	Patients with pulmonary hypertension resulting in slight limitation of physical activity. They are comfortable at rest. Ordinary physical activity causes undue dyspnea or fatigue, chest pain, or near syncope.
Class III	Patients with pulmonary hypertension resulting in marked limitation of physical activity. They are comfortable at rest. Less than ordinary activity causes undue dyspnea or fatigue, chest pain, or near syncope.
Class IV	Patients with pulmonary hypertension with inability to carry out any physical activity without symptoms. These patients manifest signs of right heart failure. Dyspnea and/or fatigue may even be present at rest. Discomfort is increased by any physical activity. Syncope or near syncope may occur.

*Only subjects with WHO Class II–IV are eligible for the study

11.1.5. 6 Minute Walk Test

In Part 1, a standard 6MWT will be performed at Screening, Weeks 6, 10, 14, and 18, including early discontinuation, and **two** 6MWTs at Week 2 as presented in the ATS guidelines (ATS Statement 2002; Appendix A). The Screening 6MWT may be obtained at baseline if the subject is known to have a 6MWD ≥ 100 meters and ≤ 450 meters. The average of the two 6MWD at Week 2 after run-in will be used as the baseline value. The subject should rest for at least 30 minutes between tests.

All 6MWTs, including those at Screening, Baseline, and post-randomization visits, should be performed in the same manner for each subject. Each subject will be provided with a carrying case with straps that will allow the device to be attached to the oxygen cylinder. During the 6MWT all subjects will be placed on oxygen at a continuous flow rate as prescribed by treating physician using an oxygen cylinder that is on a wheeled carrier. All subjects must pull the oxygen tank with the INOpulse device attached to the cylinder during all 6MWTs. Flow rate must be recorded in eCRF.

The subject should use the same oxygen tank and cart as well as the same flow rate during ALL subsequent 6MWTs, Part 1 and Part 2. If a change in the subject's oxygen supplementation is clinically indicated during the 6MWT, then during all subsequent 6MWTs the subject should use the same increased amount of LTOT administered in the same concentration or flow rate. Change in flow rate should be recorded in the eCRF.

At Screening 6MWT should be performed on oxygen with INOpulse device (turned off) attached to oxygen tank. At Week 2 6MWT should be performed on oxygen plus INOpulse device set at 15 mcg/kg IBW/hr and attached to oxygen tank.

All 6MWTs after Week 2 should be performed on oxygen plus INOpulse device set at 75 mcg/kg IBW/hr and attached to oxygen tank

In Part 2, the 6MWT will be performed at only Week 16, Week 32, and Week 52 on oxygen plus INOpulse device set at 75 mcg/kg IBW/hr and attached to oxygen tank.

11.1.6. Borg Dyspnea Scale

The Borg Dyspnea Scale, Heart Rate and SpO₂ will be recorded in Part 1 at each study visit prior to, and immediately following, the 6MWT at Screening, Weeks 2, 6, 10, 14, and 18, including early discontinuation ([ATS Statement 2002](#)) and in Part 2, at week 16, week 32 and week 52. The BDS measures perceived breathlessness on a scale of 0 (none) to 10 (maximum) and has a minimally clinically important difference (MCID) of 1 point ([Table 4](#)) ([Ries 2005](#)).

Table 4: Borg Dyspnea Score

Score	Severity
0	Nothing at all
0.5	Very, very slight (just noticeable)
1	Very slight
2	Slight (light)
3	Moderate
4	Somewhat severe
5	Severe (heavy)
6	---
7	Very severe
8	---
9	---
10	Very, very severe (maximal)

11.1.7. Vital Sign Measurements

Vital sign measurements will be performed for Part 1 at Screening, Baseline, Weeks 2, 6, 10, 14, and 18, including early discontinuation. Vital sign measurements will include heart rate (HR), respiratory rate (RR), blood pressure (BP, systolic and diastolic), and temperature. Oxygen flow rate will be recorded at each visit with estimated length of use per day.

Systemic arterial oxygenation (SpO₂) will be performed in Part 1 at Screening, Baseline, Weeks 2, 6, 10, 14, 18, and at any time of an early drug discontinuation:

- While breathing room air for at least 5 minutes
- While breathing prescribed oxygen flow rate for at least 5 minutes

- While breathing prescribed oxygen flow rate with study device/drug for at least 5 minutes to be conducted **after** week 2 (not at screening or baseline), at Week 6 through Week 18 or Early Discontinuation

In Part 2 – Vital signs and Systemic arterial oxygenation will be performed in Part 2 at Week 16, Week 32, Week 52 and Every 4 months and Early Discontinuation/End of Study.

11.1.8. Spirometry Testing and DLCO

Spirometry testing with DLCO will be assessed in Part 1 at Screening, and Week 18 and at any time of an early drug discontinuation before Week 18, and will include absolute value and percent predicted value of forced vital capacity [FVC], forced expiratory volume at 1 second [FEV₁], FEV₁/FVC ratio and DLCO.

Pulmonary Function Measurements

1. Spirometer provided for this study has to be calibrated and maintained to acceptable respiratory function standards (Miller 2005).
2. Forced-spirometry PFTs will be repeated up to 8 times to obtain 3 acceptable readings according to [ATS/ERS 2005 spirometry guidelines](#).
3. Forced-spirometry repeatability is achieved when the difference between the largest and the next largest FVC is ≤ 150 ml and the difference between the largest and the next largest FEV₁ is ≤ 150 ml. For subjects with an FVC of ≤ 1.0 L, both these values are 100 ml.
4. Total lung capacity (TLC), if results not obtained in the last 6 months, should be obtained according to ATS/ERS 2005 guidelines.
5. DLCO (diffusing capacity for the lungs measured using carbon monoxide) will be performed at Screening and Week 18, and at any time of an early drug discontinuation before Week 18. (according to ATS/ERS 2005 spirometry guidelines).

11.1.9. Physical Examination

A physical examination, including height and weight, will be performed in Part 1 at Screening to determine IBW. Physical examinations, including weight, will be performed at Week 18, and at any time of an early drug discontinuation before Week 18. A physical examination will not be required for Part 2.

11.1.10. Pregnancy Test

A pregnancy test will be performed in Part 1 at Screening Week 18, and at any time of an early drug discontinuation before Week 18. In Part 2, pregnancy testing is at the discretion of the Investigator.

Females of childbearing potential must have a negative serum or urine pregnancy test at Screening. All female subjects should take adequate precaution to avoid pregnancy by using highly effective birth control methods which include (as outlined in CTFG Contraceptive Recommendations Section 4.1):

- Combined (estrogen and progestogen containing) hormonal contraception associated

with inhibition of ovulation:

- oral
- intravaginal
- transdermal
- progestogen-only hormonal contraception associated with inhibition of ovulation:
 - oral
 - injectable
 - implantable
- intrauterine device (IUD)
- intrauterine hormone-releasing system (IUS)
- bilateral tubal occlusion
- vasectomised partner
- sexual abstinence

11.1.11. Hematology, Chemistry, Methemoglobin, NT-proBNP

Hematology laboratory tests will be performed in Part 1 at Screening and Week 18, and at any time of an early drug discontinuation before Week 18. These laboratory tests will include complete blood count (CBC) with differential and platelet count. In Part 2 will be performed at Week 52, yearly and at End of Study or Early Discontinuation.

Chemistry laboratory tests will be performed in Part 1 at: Screening and Week 18, and at any time of an early drug discontinuation before Week 18.

In Part 2, Hematology and Chemistry laboratory tests will be performed at Week 52, then on a yearly basis until EOS, or Early Discontinuation. These laboratory tests include: electrolytes (Na, K, HCO₃, and Cl), glucose, blood urea nitrogen (BUN), creatinine (Cr), aspartate aminotransferase (AST), alanine aminotransferase (ALT), gamma-glutamyl transpeptidase (GGT), alkaline phosphatase, lactate dehydrogenase (LDH), creatine phosphokinase (CPK), magnesium, bilirubin total/direct, uric acid, total protein, and albumin.

Methemoglobin levels (%) will be measured by oximetry in Part 1 at Screening and Week 2, Week 6 and at any time of an early drug discontinuation before Week 18. In Part 2 will be performed at Week 0, Week 52 and yearly including EOS or early discontinuation

NT-proBNP will be collected in Part 1 at Screening and Week 18. NT-proBNP will not be collected in Part 2

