- Survival assessment
- Completion of the SF-36
- Drug Device Dispensation
- Review Drug Device Usage
- Evaluation for symptomatic Rebound Hypertension while under medical supervision, after start of study drug and prior to sending the subject home as described in section 11.1.15

If the subject does not use the device for an average of at least 12 hours a day, the subject may not be eligible to continue to participate in the study.

If the subject continues to participate, at this visit the subject will be dispensed a 1 week supply of study drug. Additional supplies will be delivered directly to the subject's home. The used cartridges must be returned and will be picked up from the subject's home when the new supplies are delivered.

Part 1 Week 6 (Month 1), Week 10 (Month 2), Week 14 (Month 3) and Week 18 (Month 4) - the following assessments will be performed:

- Prior and concomitant medications
- WHO Functional Class
- Conduct 6 Minute Walk Test
- Borg Dyspnea scale
- Vital Signs including HR, RR, BP and temperature. SpO₂ via pulse oximetry (O₂ flow rate)
- Complete SF-36 (week 18)
- Assess AEs, SAEs, AESIs
- Medical Resource Utilization
- Lung Transplantation listing status
- Drug Device Dispensation (via home delivery)
- Review Drug Device Usage
- Spirometry testing including DLCO (week 18)
- Physical examination (week 18)
- Laboratory – Hematology and Chemistry (week 18)
- NT-proBNP (week 18)

- Pregnancy test (week 18)
- Methemoglobin (week 6)
- INOpulse Questionnaire (week 18)
- RHC subjects participating in the substudy (week 18)
- ECHO – subjects participating in the substudy (week 10 and 18)
- Survival status
- All blinded drug cartridges from Part 1 of the study must be returned to the site or Sponsor prior to dispensing open-label drug cartridges for Part 2.

Part 1 Early Term: The following visit assessments will be performed:

- Prior and concomitant medications
- WHO Functional Class
- Conduct 6 Minute Walk Tests
- Borg Dyspnea scale
- Vital Signs including HR, RR, BP and temperature. SpO₂ and methemoglobin via pulse oximetry (O₂ flow rate)
- Complete SF-36
- Assess AEs, SAEs, AESIs
- Medical Resource Utilization
- Lung Transplantation listing status
- Review Drug Device Usage
- Spirometry testing including DLCO
- RHC for subjects participating in substudy
- ECHO (for safety assessment) for ALL subjects including those not participating in ECHO substudy
- Physical examination
- Laboratory – Hematology and Chemistry
- Methemoglobin

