16.3.5. Handling Missing Data

Missing data imputation for primary endpoint:

For primary analysis, i.e. change from baseline at Week 18, missing data will not be imputed.

The following missing data imputation techniques will be employed for sensitivity analyses of primary endpoint.

- 1) Last Observation Carry Forward (LOCF) approach will be applied for subjects not withdrawing trial due to adverse events, for subjects withdrawing trial due to adverse events (including deaths), worst value (for e.g. zero for 6MWD) will be assigned at EOS visit.
- 2) Worst-case imputation approach I (i.e. impute the missing value for a subject with worst value (within the subject) for all subjects who withdraw prematurely for any reason. The value of zero for 6MWD will be imputed for all deaths.
- 3) Worst-case imputation approach II (i.e., impute the missing value for a subject in the active and Placebo dose group by the worst result of all subjects with non-missing assessments in their respective assigned dose groups). The value of zero for 6MWD will be imputed for all deaths.
- 4) Worst-case imputation approach III (i.e. impute the missing value for a subject in the active dose group by the worst result of all subjects with non-missing assessments in the same active dose groups and impute the missing value for a subject in placebo group by his/her last available assessment prior to the missing assessment. The value of zero for 6MWD will be imputed for all deaths.

Missing data imputation for secondary endpoint:

For all the other efficacy endpoints, the last observation carry forward (LOCF) approach will be used in handling the missing data as that used in the EARLY study ([Galiè 2008](#)).

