### IV. NT-proBNP:

Change in NT-proBNP (Table 10) from screening to 18 weeks.

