## 7.6 Tertiary Analysis

All tertiary analysis will be performed on ITT analysis set. No multiplicity adjustments will be done for any of the tertiary endpoints analysis. Missing data will be imputed using Last Observation Carried Forward Rule (LOCF).

For all tertiary continuous endpoints if normality assumptions fail then log transformed analysis will be performed. If the normality assumptions still fails then analysis will be performed on the ranked data.

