### 7.6.4 Change in NT-proBNP from Screening to 18 Weeks

The change from screening for log transformed NT-proBNP at Week 18 will be analyzed using ANCOVA model at week 18, with the same factors/covariates as given for secondary parameter WHO functional class (Table 30).

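### NT-proBNP has no sample between Screening and Week 18, so the planned LOCF gives every ITT subject without a Week 18 sample a change of exactly zero

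*Protocol*

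**What the plan says.** **Sampling.** Protocol 11.1.11: "NT-proBNP will be collected in Part 1 at Screening and Week 18". The same section gives hematology a further draw: "Hematology laboratory tests will be performed in Part 1 at Screening and Week 18, and at any time of an early drug discontinuation before Week" (the quote stops short of the visit number). Chemistry and methemoglobin also have an early-discontinuation measurement; NT-proBNP does not. The protocol section 11 list for Weeks 6 to 18 has "NT-proBNP (week 18"), and the early-termination list has "Laboratory – Hematology and Chemistry" but no NT-proBNP. Protocol Table 2 and SAP Table 20 agree: the NT-proBNP row is marked at Screening and Week 18 only.

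**Reference value.** SAP 4.3 item IV: "Change in NT-proBNP (Table 10) from screening to 18 weeks". SAP Table 10 names Screening as the baseline.

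**Model.** SAP 7.6.4: "The change from screening for log transformed NT-proBNP at Week 18 will be analyzed using ANCOVA model at week 18", with treatment, prostanoid use and baseline as terms. The stated alternative there is two-sided.

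**Missing data.** Protocol 16.3.5: "For all the other efficacy endpoints, the last observation carry forward (LOCF) approach will be used in handling the missing data". SAP 6.3 repeats this, and SAP 7.6 states for the tertiary endpoints: "Missing data will be imputed using Last Observation Carried Forward Rule (LOCF"). The rule that assigns zero to deaths names 6MWD only. No NT-proBNP sensitivity analysis is planned.

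**The concern.** LOCF needs a value obtained between the reference and the missing visit. NT-proBNP has none. The only value available to carry to Week 18 is the Screening value, which is also what the change is measured from, so the rule amounts to baseline carried forward.

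A subject who died, or who left because of deterioration, would be scored as stable. These constants add no information about treatment, but the ANCOVA counts them as observations. What is at stake is the size and precision of the reported NT-proBNP effect and, if drop-out differs between arms, its direction. The SAP uses no imputation for the primary analysis, so this endpoint is handled less carefully than the one it is meant to support.

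**Working it through.** **Inputs from the documents.** 150 evaluable subjects, 20% drop-out and 188 subjects at 94 per arm (SAP 5.4); two sampling times; ANCOVA on the log scale.

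**Assumptions (the documents give no figures for NT-proBNP).** SD of log change 0.7; true difference -0.40 with no placebo change, or no drug effect with both arms worsening by 0.3 or 0.1; two-sided level 0.05, because SAP 7.6.4 states a two-sided alternative without a level.

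**1. Number affected.** 150 / (1 - 0.20) = 187.5, rounded up to 188, which reproduces the plan's figure. 188 - 150 = 38, and 38/188 = 20.2%. This is an upper figure, since some subjects who stop drug will still give a Week 18 sample.

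**2. Imputed value.** log(Screening) - log(Screening) = 0.

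**3. What LOCF estimates.** With missing fractions dA and dP and true mean changes mA and mP, the estimate targets (1 - dA)mA - (1 - dP)mP. With 20% missing in each arm, the true difference is multiplied by 0.80: -0.40 becomes -0.32.

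**4. Standard error.** The variance in one arm after LOCF is (1 - d)SD² + d(1 - d)m².
- iNO: 0.8 × 0.49 + 0.16 × 0.16 = 0.4176
- Placebo: 0.8 × 0.49 = 0.392
- LOCF SE = √[(0.4176 + 0.392)/94] = 0.093
- Observed-case SE = 0.7 × √(2/75) = 0.114 (simulated ANCOVA: 0.114 to 0.115)
- SE if all 188 had really been sampled = 0.7 × √(2/94) = 0.102

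The LOCF standard error is thus smaller than complete data would give. Estimate and SE shrink together: 0.32/0.093 = 3.4 against 0.40/0.114 = 3.5. Simulated power is about 93% either way.

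**5. Unequal drop-out, no drug effect, drop-out unrelated to outcome.** Bias = m[(1 - dA) - (1 - dP)], with the SE from step 4. The two-sided error is the sum of the two normal tails beyond ±1.96, centred at bias/SE.

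| Worsening in both arms | Drop-out iNO / placebo | Bias | LOCF SE | Two-sided error |
|---|---|---|---|---|
| 0.3 | 30% / 10% | -0.06 | 0.093 | 9.4% + 0.5% = 9.9% |
| 0.3 | 25% / 15% | -0.03 | 0.093 | 5.1% + 1.1% = 6.2% |
| 0.1 | 30% / 10% | -0.02 | 0.092 | 4.1% + 1.5% = 5.6% |
| 0.3 | 10% / 30% | +0.06 | 0.093 | 9.9%, now against iNO |

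Simulated ANCOVA gave 9 to 11% for the first row. Observed cases stay near 5% throughout.

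**6. Drop-out linked to worsening.** Take a latent correlation of 0.5 between worsening and drop-out, with worsening 0.3, 30% / 10% drop-out and no drug effect. The mean among those who stay falls by 0.5 × 0.7 × φ(z)/(1 - d), where z is the normal quantile at 1 - d.
- iNO: 0.35 × 0.348/0.7 = 0.174
- Placebo: 0.35 × 0.1755/0.9 = 0.068
- Observed-case bias = -0.174 + 0.068 = -0.106
- LOCF bias = 0.7 × (0.3 - 0.174) - 0.9 × (0.3 - 0.068) = -0.12

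Simulated two-sided error is about 28% with LOCF and 16% with observed cases. Dropping LOCF helps but does not cure this.

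**The case against.** **Not every drop-out is affected.** A reader might infer that every drop-out is set to zero. Protocol 10.1 encourages subjects who stop study drug to complete assessments to Week 18, and those who attend have an observed value. Run-in failures are outside the ITT set. Only ITT subjects with no Week 18 sample are affected. This stands.

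**LOCF might mean post-baseline values only.** Nothing would then be carried, and the analysis would already be observed-case. Neither document says so, and if that is the intent, it has to be written down.

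**At the plan's own drop-out rate, inference hardly changes.** The 20% is not split by arm. With equal drop-out the test is essentially unaffected and the estimate is pulled towards zero. This stands for the test, but not for the reported effect and its interval.

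**A general claim of inflated type I error goes too far.** The error rates need unequal drop-out together with worsening in both arms, and neither is in the documents. With worsening of 0.1 the rate is near nominal. Quoting them against a one-sided 2.5% would also overstate the inflation: the protocol's one-sided default applies only where nothing else is specified, and SAP 7.6.4 specifies a two-sided alternative.

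**Omitting subjects is not neutral either.** This is correct, as step 6 shows, and it is why a sensitivity analysis belongs in the fix.

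**Conclusion.** The point holds for ITT subjects without a Week 18 NT-proBNP sample. For them the written rule produces a change of exactly zero, deaths included. That result needs no assumption beyond reading LOCF as written.

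The 20% dilution follows from the planned drop-out if it is equal between arms. The standard errors and error rates rest on the assumed SD, effect, worsening and drop-out split. The bias can favour either arm; the documents give no reason to expect it to favour iNO.

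It would be wrong to infer any threat to the trial's main conclusion. NT-proBNP is one of nine tertiary endpoints, has no multiplicity adjustment, and lies outside the gatekeeping sequence of 6MWD, TTCW and WHO class. The change should be made because it is cheap and the reported NT-proBNP estimate is otherwise misleading.

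**What to change.** Before unblinding:

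- Exempt NT-proBNP from LOCF in SAP 6.3, 7.6 and 7.6.4 and in protocol 16.3.5, or record the departure in SAP 11.0, whose table is empty.
- Analyse observed Week 18 log values with the planned ANCOVA.
- Add a sensitivity analysis by multiple imputation, using treatment, screening NT-proBNP, prostanoid use, and post-baseline 6MWD and WHO class. The last two are collected at Weeks 6, 10 and 14, so they carry information on deterioration before drop-out.
- Report by arm the deaths and the number of subjects with no Week 18 sample, next to the NT-proBNP result.
- In the same edit, reconcile SAP 6.4, which makes Week 2 the baseline for all efficacy analyses except SF-36, with SAP Table 10; no NT-proBNP sample exists at Week 2.

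**Cost.** Text changes in both documents (or one SAP 11.0 entry), an imputation model to specify, fewer subjects in the main NT-proBNP analysis, and a wider but honest standard error. In the equal drop-out case there is no loss of power. No visit or blood draw is added.

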11.1.12. Eligibility of INOpulse Device Usage

Subjects will be required to demonstrate an average daily usage ≥ 12 hours (rounded to the nearest hour) with no more than 2 days of usage < 8 hours per day of the INOpulse device during the initial 2 week run-in period of the study in order to be eligible to continue to the treatment phase. Calculation of compliance: First day and last day's data during the run-in period does not count towards compliance data. This assessment will occur during the Run-in period at Week 2 in Part 1.

11.1.13. Right Heart Catheterization

A RHC may be performed under the following circumstances in Part 1:

- A RHC will be performed in a subset of approximately 50 subjects at selected sites. The RHC performed at Baseline will be used as entrance criteria. A repeated RHC will be performed at Week 18 to assess changes in pulmonary hemodynamics. RHC at Week 18 should be performed while the subject is in stable condition and on study drug for at least 30 minutes prior to the start of the procedure.
- For subjects who are not included in this subset who have not had a RHC within the previous 5 years that meet eligibility criteria and are otherwise eligible, a RHC will be conducted at Screening.
- Subjects in the subset who discontinue study drug prior to Week 18 will have a RHC performed at time of study drug discontinuation rather than Week 18..

